7.3 Treatment Assignment

Patients will be randomized 1:1 to receive open-label treatment with SEL-212 or KRYSTEXXA.

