13.1 Sample Size Determination

The primary efficacy criterion in this study is defined as the percentage of subjects who achieve and maintain reduction of SUA < 6 mg/dL for at least 80% of the time during Treatment Period 3 and Treatment Period 6.

The percentage of responders according to the above criterion is assumed to be 65% in the SEL-212 arm and 44% in the KRYSTEXXA arm.

Using the Chi-square test for comparison between the SEL-212 arm and the KRYSTEXXA arm, and considering a one-sided alpha=5% and the statistical power of 80%, results in 69 subjects per treatment group. Taking into account that some subjects may be excluded from the modified Intent-to-Treat (mITT) analyses (Section 13.2.4), 75 subjects per treatment group will be randomized. For the sample size estimation, Chi-square test, instead of the Cochran-Mantel-Haenszel test, is used although the randomization will be stratified for tophus presence (yes/no) as there is no valid assumption of the distribution of this stratification variable within the eligible subject population.

Sample size calculations were performed with the software package nQuery Advisor® Sample Size Calculator V. 8.2.1.0.

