6.1. Patient Disposition and Withdrawals

Patient disposition data will be listed. Summary tables reflecting the number of patients for the following will be presented:

- Screened (or Enrolled) patients
- ITT, SS, mITT, and PP patients
- Patients who complete the study treatment
- Patients who early terminate the study treatment and reasons for early termination
- Patients who early terminate the study and reasons for early termination

Screen Failure patients will be listed.

Kaplan-Meier (KM) figures of the time to early termination of the study by treatment group and by presence of tophus will be provided.

Kaplan-Meier (KM) figures of the time to early termination of the study due to adverse event by treatment group and by presence of tophus will be provided.

Kaplan-Meier (KM) figures of the time to early study treatment discontinuation by treatment group and by presence of tophus will be provided.

Kaplan-Meier (KM) figures of the time to early study treatment discontinuation due to stopping rules by treatment group and by presence of tophus will be provided.

Kaplan-Meier (KM) figures of the time to early study treatment discontinuation due to stopping rules or due to Infusion-related reactions including infusion reaction, allergic reaction to pre-med or one of drug components and anaphylaxis, by treatment group and by presence of tophus will be provided.

In addition, stratified Log-rank test will be used to test treatment difference with presence of tophus as stratification factor for those time to event endpoint mentioned above. Unstratified Log-rank test will be used to test treatment difference for patients with presence of tophus and for patients with absence of tophus.

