7.4. Deviation from Analyses Planned in Protocol

7.4.1. Additional analyses

The following analyses are added even though they are not included in the protocol:

- Interim analysis.
- Subgroup analyses on the secondary endpoint by patient's primary efficacy endpoint (responder vs. non-responder).

The following analyses have been added as a result of the impact of Covid-19 on the study which may result in a larger anticipated number of subjects not completing the study and therefore not undergoing the assessments required for the primary efficacy endpoint or the study being stopped prematurely by sponsor decision. This is in line with FDA Guidance on Conduct of Clinical Trials of Medical Products during COVID-19 Pandemic Guidance for Industry, Investigators, and Institutional Review Boards.

- Additional analyses suggested to primary endpoint as sensitivity analyses to determine if the impact that these have on the conclusions of the study and to describe the impact of Covid-19 on the study performance.
- A sensitivity analysis which limited the analysis to results processed in the central laboratory to determine if this resulted in different conclusions to those found from the full analysis to determine consistency in laboratory testing between central and local laboratories.
- Kaplan-Meier analysis of withdrawal from study by treatment arm and presence of tophus to determine if subjects withdraw from the study in different proportions and at different rates within the treatment groups and depending on the presence of tophus.
- Kaplan-Meier analysis of withdrawal from study due to an adverse event by treatment arm and presence of tophus to determine if subjects experience adverse events in different proportions and at different rates within the treatment groups and depending on the presence of tophus.
- Poisson regression with number of gout flares experienced during treatment periods 1-6 as the dependent variable, treatment and the presence of tophus as independent variables and length of follow up as a covariate. The ITT population would be used to conduct this analysis. Similar analysis is done for periods 4-6.

This document is confidential.

8. Safety

The population used for safety analyses will be the Safety Set (SS). Safety will be assessed on the basis of adverse event (AE), clinical laboratory data, ECG parameters, physical examinations, and vital signs.

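### The log-rank tests in SAP 6.1 cannot show whether withdrawal depends on tophus, although SAP 7.4.1 gives that as a purpose of the withdrawal analyses

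*SAP*

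**What the plan says.** SAP 6.1 plans Kaplan-Meier figures, by arm and by tophus, for five times to event: leaving the study, leaving it because of an adverse event, stopping study drug early, stopping it under the stopping rules, and stopping it under those rules or for an infusion-related reaction. Two kinds of test go with them. Overall, a "stratified Log-rank test will be used to test treatment difference with presence of tophus as stratification factor". Within each tophus group, "Unstratified Log-rank test will be used to test treatment difference for patients with presence of tophus and for patients with absence of tophus". SAP 6.1 states no significance level, no sidedness and no rule for reading the two within-group results together.

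SAP 7.4.1 states a purpose for two of the five. The Kaplan-Meier analysis of withdrawal from study is to determine whether "subjects withdraw from the study in different proportions and at different rates within the treatment groups and depending on the presence of tophus". The bullet on withdrawal due to an adverse event is worded in parallel. It speaks of subjects having adverse events, again at "different rates within the treatment groups and depending on the presence of tophus". Neither section plans a treatment-by-tophus interaction or a test of tophus itself.

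**The concern.** Dependence on tophus can mean two things: that the arm effect differs between patients with and without tophi, or that tophus itself is associated with withdrawal. The planned tests address neither. The stratified log-rank test conditions tophus out. Each within-group test has the null of no arm difference in that group.

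The only p-value route left to the stated question is to set one group's result against the other's. That comparison is driven largely by the number of events in each group, and the groups may be unequal. A report could then say that one drug is better retained only in tophaceous patients, or only in the others, when the arm effect is the same in both.

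**Working it through.** **Inputs from the documents.** Protocol 7.3: "Patients will be randomized 1:1 to receive open-label treatment with SEL-212 or KRYSTEXXA". Protocol 13.1: "75 subjects per treatment group will be randomized", with response "assumed to be 65% in the SEL-212 arm and 44% in the KRYSTEXXA arm". Treatment lasts 168 days (Protocol 7.1). Protocol 13.1 says that the tophus distribution cannot be assumed. Protocol 5.4 cites about 70% with a tophus as background. I use 50% to 80%.

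**The plan's own figure.** Protocol 13.1 gives "one-sided alpha=5% and the statistical power of 80%, results in 69 subjects per treatment group". With mean rate 0.545 and pooled variance under the null:

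n = [1.645·√(2·0.545·0.455) + 0.842·√(0.65·0.35 + 0.44·0.56)]² / 0.21² = 68.5, so 69 per arm.

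This reproduces the plan. It concerns the primary endpoint only; the documents give no event rate or power for the withdrawal tests.

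**Chance that exactly one tophus group is significant when the hazard ratio (HR) is the same in both.** For assumed event proportions f1 (SEL-212) and f0 (KRYSTEXXA):

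- HR = ln(1−f1)/ln(1−f0); total events D = 75·(f1+f0); a group with share s has s·D events.
- Power in a group (Schoenfeld) = Φ(|ln HR|·√(sD/4) − z), with z = 1.645 (one-sided 5%) or 1.960 (two-sided 5%).
- The groups contain different patients, so P(exactly one) = p1(1−p2) + p2(1−p1).

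Worked case, 35% vs 56%, 70% with tophus, one-sided: HR = 0.431/0.821 = 0.52 and D = 68.25, giving 47.8 and 20.5 events. Powers are 0.720 and 0.426. P = 0.720·0.574 + 0.426·0.280 = 0.53. Two-sided, the powers are 0.606 and 0.309 and P = 0.54.

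| Assumed event rates, SEL-212 vs KRYSTEXXA | HR | Events | Exactly one significant, two-sided 5% | One-sided 5% |
|---|---|---|---|---|
| no arm difference | 1.00 | any | 9.5% | 9.5% |
| 10% vs 15% | 0.65 | 18.75 | 18–19% | 27% |
| 20% vs 30% | 0.63 | 37.5 | 29–30% | 39–40% |
| 30% vs 45% | 0.60 | 56.25 | 40–44% | 48–52% |
| 35% vs 56% | 0.52 | 68.25 | 50–59% | 48–59% |
| 20% vs 50% | 0.32 | 52.5 | 29–55% | 19–43% |

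Ranges run over 50% to 80% with tophus. The first row is 2·0.05·0.95. The 35% vs 56% row is one minus the planned response rates.

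**Check by simulation** (exponential times, 150 patients, 5,000 trials per scenario, 50% or 70% with tophus). At 35% vs 56% and 70% tophus, exactly one group was significant in 53% of trials, one- or two-sided. At 20% vs 30% it was 38–39% one-sided and 28–29% two-sided. With no arm difference it was 9–10%. The 10% vs 15% row rests on the formula alone. A two-sided 5% interaction contrast in the same trials rejected in 3.5% to 5.4%.

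**What an interaction test could detect.** SE of the log ratio of HRs = √(4/D₁ + 4/D₀), with D₁ and D₀ the events in the two tophus groups. At 70% tophus and 68.25 events this is √(4/47.8 + 4/20.5) = 0.53. A ratio of HRs of exp(2.80·0.528) ≈ 4.4 is then needed for 80% power (two-sided 5%). With 18.75 events the SE is √(4/13.1 + 4/5.6) = 1.01, and the ratio needed is about 17.

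**Sparse cells.** If withdrawal for adverse events is 5% vs 10% (assumed), the chance that at least one arm-by-tophus cell has no events at 80% tophus (60 and 15 per arm) is 1 − (1−0.95¹⁵)(1−0.90¹⁵)(1−0.95⁶⁰)(1−0.90⁶⁰) ≈ 59%. At 70% it is about 42%. An ordinary Cox interaction estimate can then be infinite.

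**The case against.** The within-group tests are valid for the null they state, and SAP 6.1 claims no more for them than a comparison of arms. The wording about dependence on tophus belongs to the Kaplan-Meier analyses. It covers only the two study-withdrawal endpoints and does not name the log-rank tests. Curves by arm and tophus are a legitimate descriptive answer. The SAP nowhere says that the two p-values will be compared. All of this stands. What remains is that these tests are the only inference attached to the curves, and they leave the stated question untested.

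A reader might infer that about half of trials with no tophus dependence would appear to show it. The documents do not support that as a general figure. It needs a true arm difference about as large as the one planned for response. Non-response is at most a proxy for stopping treatment, not for leaving the study, because patients taken off drug continue visits to the end of Treatment Period 6 (Protocol 7.4.1.1 and 7.4.1.2). The documents give no study-withdrawal rates.

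A reader might also see the higher percentages as an inflated type I error of the planned tests. They are not. Where the arms truly differ in both groups, each significant result in the right direction is a correct rejection, and discordance reflects limited power. Even with no arm difference, two 5% tests disagree 9.5% of the time.

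**Conclusion.** The point holds as a gap between a stated purpose and the planned tests. No planned test addresses effect modification by tophus or the effect of tophus on withdrawal, and discordant within-group p-values cannot stand in for one. Discordance under a common hazard ratio runs from 9.5% with no arm difference to 48–59% at 35% vs 56%, with the study-withdrawal endpoints plausibly nearer the lower figures. Every event rate and the tophus share are assumed. The figures also depend on a significance level and sidedness that the SAP does not give. They are not bounds: a wider grid (15 to 80 events, HR 0.3 to 1.0) gives about 3% to 63%.

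It would go too far to call the within-group tests wrong, or to say that the SAP sets the tophus question for all five endpoints. The interaction model is useful for all five, but the stated purpose covers two. These are supportive disposition analyses. The primary test and the sample size are not affected.

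**What to change.** In SAP 6.1, add for each time-to-event endpoint a Cox model with treatment, tophus presence and their interaction. Use a Firth penalty or profile-likelihood intervals where an arm-by-tophus cell has few or no events. Report the hazard ratio with 90% CI in each tophus group, the tophus effect, and the ratio of hazard ratios with its CI and p-value.

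Keep the stratified log-rank test for the overall arm comparison and keep the Kaplan-Meier curves by tophus. Label the within-group log-rank tests descriptive. State that dependence on tophus is not inferred from one group being significant and the other not.

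The cost is SAP wording and one extra model per endpoint, with no new data. The downside is low power for interaction, so the answer will often be that the question is not resolved.

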6.2. Demographic and Other Baseline Characteristics

Demographic characteristics such as gender, age, race and ethnicity will be summarized for all ITT patients, by treatment and overall. Demographic characteristics will be also summarized using MITT and PP set patients.

Age will be calculated based on date of signed informed consent as below:

(Date of informed consent - date of birth) / 365.25 and truncated to complete years

6.3. Medical History

No summaries will be provided. Medical history will be coded using current version of Medical Dictionary for Regulatory Activities (MedDRA®). The version number will be noted on the actual data listing for medical

This document is confidential.

history. Medical history will be listed by treatment and patient including coded terms for system organ class and preferred term.

6.4. Concomitant Medication and Therapy

Concomitant medications are permitted during this study unless otherwise restricted. Medications used in the 3 months prior to screening and during the study will be recorded on the Concomitant Medications electronic case report form (eCRF). The reported medications will be reviewed and evaluated by the investigator or designee to determine if they affect a patient's eligibility to participate or continue to participate in the study.

6.4.1. Prior Medication

Prior medication is defined as any medication which has an end date prior to the date of first dose of study drug administration.

Prior medication will be listed.

6.4.2. Concomitant Medication

Concomitant medication is defined as any medication which has an end date after the date of first dose of study drug administration or missing.

The original verbatim terms collected in the eCRF for prior and concomitant medications will be coded using the World Health Organization Drug Dictionary (WHO-DD current version) into drug class (Anatomical Therapeutic Classification [ATC] level 4) and preferred term.

Concomitant medication will be summarized by treatment, ATC4 and preferred term for SS patients and will be listed for all SS patients.

This document is confidential.

7. Efficacy

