10.6 Administration

10.6.1 SEL-212

Before administration of SEL-212, patients will be premedicated with antihistamines and steroids as described in [Section 10.5](#).

Patients will receive treatment with SEL-212 on Day 0 of each Treatment Period for a total of 6 doses of study drug.

All study drugs should be administered through the same IV access. All blood samples should be drawn from an alternative venous access.

If an infusion reaction occurs, Investigators are permitted to use concomitant medications or treatments deemed necessary to provide adequate patient care. Investigators should also utilize the infusion reaction lab kit provided in the Study Operations Manual to collect additional blood specimens. In the case of a Grade 3 or 4 infusion reactions occurring during an infusion, the administration of study drug should be immediately discontinued, and the affected patient should be treated according to the clinical trial site's protocol for infusion reactions (e.g., monitoring, administration of antihistamines, corticosteroids, fluids and epinephrine, as clinically indicated).

The reconstituted SEL-110.36 will be withdrawn from the vial and dosed via IV infusion with a syringe infusion pump utilizing an appropriately sized syringe. SEL-110.36 will be infused at a rate of 3.0 mL/hr for the first 30 minutes, then a rate adequate to deliver the remaining dose volume over a period of 60 minutes concurrently with 125 mL normal saline. Following the infusion of SEL-110.36, the main IV line must be flushed with normal saline prior to the start of the SEL-037 infusion. Refer to the Study Operations Manual for instructions regarding infusions for patients with medical history involving cardiovascular comorbidities.

SEL-037 infusion will start within 15 minutes after completion of the SEL-110.36 infusion. SEL-037 will be infused via infusion pump over a time period of no less than 120 minutes. If an infusion reaction occurs during the administration of SEL-037, the infusion may be slowed, or stopped and restarted at a slower rate at the discretion of the physician. Following the infusion of SEL-037, the main IV line must be flushed with normal saline.

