5.8. Key Definitions

Baseline is defined as the last non-missing value prior to the start of infusion of SEL-212 or KRYSTEXXA®.

Day 0 of Treatment Period 1 is defined as the first date of study drug administration.

Study day within each treatment period will be calculated as date of event/collection – first dose date at each treatment period to be consistent with protocol defined day 0.

Overall study day will be calculated as date of event/collection – first dose date of the study.

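### A medication that ends on the first dosing day is neither prior nor concomitant under the SAP's definitions, so it appears in neither the summary nor the listings

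*SAP*

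**What the plan says.** The two categories are defined by end date only.

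- SAP 6.4.1: "Prior medication is defined as any medication which has an end date prior to the date of first dose of study drug administration". The only output is a listing: "Prior medication will be listed".
- SAP 6.4.2: "Concomitant medication is defined as any medication which has an end date after the date of first dose of study drug administration or missing". The outputs are a table and a listing: "Concomitant medication will be summarized by treatment, ATC4 and preferred term for SS patients and will be listed for all SS patients".

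The reference point is a calendar date. SAP 5.8 states: "Day 0 of Treatment Period 1 is defined as the first date of study drug administration". Neither rule uses the medication's start date or a clock time.

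The data themselves are collected. SAP 6.4 says: "Medications used in the 3 months prior to screening and during the study will be recorded on the Concomitant Medications" eCRF page, and use during the study includes the first dosing day.

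The protocol treats drugs given for an infusion reaction as concomitant. Section 10.6.1 (SEL-212) says: "If an infusion reaction occurs, Investigators are permitted to use concomitant medications or treatments deemed necessary to provide adequate patient care". Section 10.6.2 repeats this for the KRYSTEXXA arm.

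**The concern.** One rule is strictly before the first-dose date and the other strictly after it, so the date itself is left over. That date is one on which single-day drugs are expected. Protocol 10.5.2 places a fexofenadine dose and an intravenous methylprednisolone dose on the day of dosing. Protocol 10.6.1 and 10.6.2 allow drugs to treat an infusion reaction, with antihistamines, corticosteroids, fluids and epinephrine among their examples for severe reactions. Protocol 12.2.1.5 counts a drug-related event as an infusion reaction if it falls within 24 hours of the start of the infusion, so one-off treatment can easily begin and end on the dosing date.

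At stake is the completeness of a safety display. A patient who receives one-off treatment for a reaction to the first infusion and is not dosed again could show no such treatment in the concomitant medication table or in either listing, although the protocol calls that treatment concomitant. A patient who receives the identical treatment at the second infusion would be shown.

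**Working it through.** The plan gives no figure to reproduce. The check is whether the two definitions cover every possible end date once and only once.

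**Inputs.** The prior rule (SAP 6.4.1), the concomitant rule (SAP 6.4.2) and the first-dose date (SAP 5.8). Let d be the end date minus the first-dose date, in days.

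- Prior: d < 0.
- Concomitant, as written: d > 0, or end date missing.
- Concomitant, as proposed: d ≥ 0, or end date missing.

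| End date | Prior? | Concomitant, as written? | Concomitant, as proposed? |
|---|---|---|---|
| d = -2 | yes | no | no |
| d = -1 | yes | no | no |
| d = 0 | no | **no** | yes |
| d = +1 | no | yes | yes |
| d = +2 | no | yes | yes |
| missing | no | yes | yes |

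As written, d = 0 is the only uncovered case. With the proposed rule every case falls in exactly one category, with no gap and no overlap.

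**Is the case assigned elsewhere?** I found no other section of the SAP or protocol that places a medication ending on the first-dose date.

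**What is and is not affected.**

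- Lost: a record ending on Treatment Period 1 Day 0, whatever its start date. This includes single-day reaction treatment and any Day 0 premedication recorded on the same eCRF page.
- Kept: treatment that runs into the next date, treatment with a missing end date, and same-day treatment at any later infusion.
- Partly masked: the SAP's table conventions (11.2.5.2) present numbers and percentages of patients. A patient who takes the same preferred term again on a later date is still counted under that term.

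**The case against.** The case against giving this weight is strong, and most of it stands.

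First, the table is only descriptive. SAP 6.4.2 names no test, no indication and no infusion-reaction subset. Antihistamines and steroids are also given to all patients as premedication (Protocol 10.5.2), so even a corrected table could not show which doses treated a reaction. A reader might infer that a planned between-arm comparison of reaction treatment is compromised, but the documents plan no such comparison.

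Second, the reactions are reported elsewhere. They are adverse events of special interest (Protocol 12.2.1.5). SAP 8.3 summarises these events, treatment-emergent events and events leading to study drug withdrawal. SAP 6.1 adds Kaplan-Meier figures and a stratified log-rank test for treatment discontinuation due to stopping rules or infusion-related reactions. None of these uses the concomitant medication definition.

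Third, a reader might infer unequal loss. One date out of up to 6 planned infusions on SEL-212 is 1/6 = 16.7%, against 1/12 = 8.3% on KRYSTEXXA. Those are shares of planned infusion days. They become shares of lost records only if treated reactions are spread evenly over all planned infusions and every patient receives them all. The documents do not support this. Protocol 5.5 ties pegloticase reactions to high antibody titer, typically after urate control is lost, and the stopping rules in Protocol 7.4.1 end dosing early. The SEL-212 rule can withdraw a patient after one infusion, whereas the KRYSTEXXA rule needs two consecutive pre-dose values and excludes the one before the first dose. That is a structural reason why patients with a single infusion could be more common on SEL-212, but it does not say how many of them had a treated first-infusion reaction.

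What survives is the definitional gap itself. It might be said that programmers will resolve it, but they could assign the Day 0 records to either category and the SAP does not say which.

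**Conclusion.** The gap is certain on the text: an end date equal to the first-dose date satisfies neither definition. If the rules are programmed as written, these records are absent from the by-treatment summary and from both medication listings, although the protocol regards reaction treatment as concomitant. This rests on reading the two rules literally and as comparisons of calendar dates, which is how they are worded.

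The importance is minor. The loss is confined to one date per patient, in a descriptive safety table, and the records remain in the database. Its size cannot be computed, nor can any difference between arms, because the documents give neither the rate of treated first-infusion reactions by arm nor the expected number of patients with only one infusion. The documents support no conclusion about bias in the safety comparison or any effect on efficacy.

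**What to change.** In SAP 6.4.2, define concomitant medication as any medication with an end date on or after the first-dose date, or missing. Leave SAP 6.4.1 unchanged. Where stop times are recorded, flag Day 0 records that ended before the start of the first infusion, so that pre-infusion use can be told apart from treatment given during or after it.

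The cost is a few words in the SAP and one comparison operator in the program, with no extra data collection. The downside is that drugs stopped on Day 0 before the infusion, such as that day's premedication if it is recorded there, are also counted as concomitant. Where no time is recorded the flag cannot separate them.
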